1.0 Objectives

1.1 Study Objectives

In the previous cycle of this grant, we characterized hemisphere specific motor control deficits in the non-paretic arm of unilaterally lesioned stroke survivors. Our preliminary data indicate that functional performance in the non-paretic arm, measured by the Jebsen-Taylor Hand Function Test (JTHFT), is diminished in patients with **severe paresis** by on average, 66% following right-hemisphere damage and 115% following left hemisphere damage. We hypothesize that such large deficits in the non-paretic arm interfere with the performance of functional activities in patients with severe paresis, who also cannot use the paretic arm for prehension and manipulation.

We have specifically designed an intervention to remediate the hemisphere-specific deficits in the non-paretic arm, using a virtual-reality platform. We then facilitate generalization and transfer to functional behaviors encountered in the natural environment by training speed and accuracy of manipulation using a variety of real objects. This intervention protocol is grounded in the premise that targeted remediation of fundamental control deficits exhibited by the non-paretic arm will generalize beyond practiced tasks to functional activities and functional independence. This intervention contrasts with the more typical approaches focused on paretic arm improvements, and the more pragmatic task-specific training therapies of essential ADL's which we argue is limited in scope, more cumbersome and ignores known fundamental motor control deficits. The impact of the proposed research is that we address persistent functional performance deficits in chronic stroke patients with severe paresis, who's non-paretic arm impairments are generally ignored in most current rehabilitation protocols. We propose a 2-site, two-group randomized intervention with a treatment group, which will receive unilateral training of the non-paretic arm, through our **Virtual Reality and Manipulation Training (VRMT)** protocol. The control group will receive a comparison intervention, designed to match the experimental intervention in duration and frequency, but employs conventional therapies according to recently released practice guidelines for upper limb intervention in adult stroke. This proposal combines the research and recruiting strengths of two active laboratories, each with a history of studying hemisphere specific motor deficits in stroke survivors ([name] and [name]), and stroke clinical trial intervention research ([name]). We have already integrated our laboratories to conduct the pilot research that provides support for the predictions of the first two aims, detailed below.

Aim 1: To determine whether non-paretic arm VRMT in chronic stroke survivors with severe paresis will produce durable improvements in non-paretic arm motor performance that will generalize to improve functional activities and functional independence to a greater extent than conventional therapy focused on the paretic arm. We predict that: 1a) Unilateral VRMT training of the non-paretic arm will produce functional improvements in non-paretic arm motor performance (JTHFT), 1b) Conventional therapy focused on the paretic arm should decrease paretic arm impairment (Fugl-Meyer) to a greater or equal extent than non-paretic arm VRMT. We will assess paretic arm impairment level using the upper extremity component of the Fugl-Meyer Assessment (UEFM) as our primary measure, and "work area" using kinematic analysis, as detailed by Dewald and Co-workers [5] as our secondary measure. 1c) The effects of non-paretic arm VRMT will generalize to functional activities (Abilhand) and functional independence (FIM-motor/Barthel) to a greater extent than conventional paretic arm therapy. This aim provides a strong test of our hypothesis that non-paretic arm motor training will have a greater impact on functional independence than conventional paretic arm training in patients who lack paretic hand function, a prediction supported by our pilot data (see Figure 8).

Aim 2: To determine whether intervention-induced improvements in non-paretic arm performance are associated with improvements in hemisphere-specific reaching kinematics. We predict that VRMT-induced improvements in performance will be correlated with reductions in hemisphere-specific motor deficits [6-9], which are targeted by the VR component of our intervention. We will test this using a planar reaching paradigm that we developed and employed in the previous cycle of this grant for

quantifying hemisphere-specific non-paretic arm kinematics [6]. We predict that improvements in functional performance (JTHFT) will correlate better with *early trajectory variance* in LHD patients, but with *late trajectory variance* in RHD patients. These variables have previously been associated with left and right hemisphere processes, respectively.

Aim 3: To determine whether our experimental intervention (non-paretic arm VRMT) might have detrimental effects on paretic arm impairment (Fugl-Meyer, Kinematics). We predict that VRMT dependent improvements in non-paretic arm motor performance **will not decrement** paretic arm impairment level, a prediction supported by our pilot data (Figure 7) and the findings of Urbin et al [10]. This aim is important to ensure that VRMT of the non-paretic arm does not have a negative effect on paretic arm function. *Our pilot data from 15 severely paretic patients supports this hypothesis, indicating that VRMT remediation of the non-paretic arm leads to modest reductions in paretic arm impairment.*

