1.2 Primary Study Endpoints

Non-Paretic Arm Evaluation: Jebsen-Taylor Hand Function Test
Paretic Arm Evaluation: Upper-Extremity Fugl-Meyer Assessment
Upper Extremity Functional Activity: Abilhand Assessment
Functional Independence: Barthel Index

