Importantly, our proposed intervention focuses on patients with severe paresis who are in the chronic phase of stroke, and who do not have the sensorimotor requisites for paretic hand dexterity or manipulation. In this group of patients, recent findings indicate that intense resistance training of the non-paretic arm can reduce impairment measured in the paretic arm [10]. Consistent with this finding, our pilot data shows that intense non-paretic arm dexterity training also leads to a modest reduction in paretic arm impairment. Thus, we expect that the unilateral non-paretic arm VRMT training proposed here will improve functional independence without jeopardizing paretic arm function in patients with severe paresis (Aim 3). Our ultimate goal is to determine whether non-paretic arm remediation should be part of a package of rehabilitation that assesses and remediates fundamental control deficits in each arm of severely paretic stroke patients [4].

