8.2 Sample size determination

Based on our primary outcome measures (Barthel, FIM-motor, Abilhand, UEFM, JTHFT) the proposed sample size of 60 participants per group provides adequate power (≥ 0.80) to assess each prediction when the effect size (Cohen's f) is 0.35 or greater. Cohen suggested that researchers consider $f=0.1$ as a small effect, $f=0.25$ as a medium effect, and $f=0.4$ as a large effect. To determine sample size, we used a power analysis program, SOLO [81], and computer simulation. SOLO permitted us to vary effect sizes and determine the test's power for a fixed group size. The simulation permitted us to use our pilot data to generate multivariate normal data; fit a model with fixed effects for group, test, and group by test interaction; conduct tests to include those for the linear contrasts; and record the p-value and associated effect size. The pilot data was particularly useful because the participants had been chosen so that they would span the expected impairment levels, and included right- and left-hemisphere-damaged participants. We will go through the major measures and analyses for each aim below. We have collected pilot data for 15 participants, using a cross-over design, for Aims 1 and 2, which provide preliminary support for our predictions.

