8.3 Statistical methods

To assess our intervention, we will fit linear mixed models (LMMs) with single-degree-of-freedom linear contrasts [80] to determine if the data support our predictions (see next section). We will use a linear mixed model with main effects for group (experimental, control) and time (Test) and the group by time interaction simply provides a more flexible approach to the typical analysis of variance (ANOVA) model for a randomized pretest-posttest design. Specifically, LMMs will permit us to account for participant matching with a random cluster effect; and they permit each participant to have her or his initial value (random intercept) and different change patterns across the tests (random coefficients for an underlying piecewise regression). LMMs allow us to use covariates to adjust for any potential confounders. Finally, these models can tolerate missing data on the response, which is not true of the standard ANOVA-based model.

Lesion Reconstruction Methods: [name]'s laboratory personnel will reconstruct stroke lesions from the research grade MRI scans. They will superimpose lesions on each axial slice to identify common areas of lesion overlap associated with damage to the right or left hemisphere and to assess comparability of intrahemispheric lesion location in our two tracks. This grant will not specifically examine intrahemispheric lesion location, but these data will provide pilot data for future studies. To calculate the CST lesion load, we will use the tractography based atlas of human brain connections from the natbrain lab [72]. We will use the MRICron descriptive tool for the calculation of the CST-lesion overlap volume. The binary lesion mask file will be overlaid onto either the left or right binary template CST atlas, and the percentage of CST which overlaps with the lesion is calculated.

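### Aim 3 predicts no worsening of the paretic arm, but the plan states only difference contrasts, and a non-significant contrast alone cannot support that prediction

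*Combined protocol and SAP*

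**What the plan says.** Aim 3 (section 1.1) asks whether VRMT "might have detrimental effects on paretic arm impairment (Fugl-Meyer, Kinematics"), predicts that improvement in the non-paretic arm "will not decrement" the paretic arm, and gives its purpose as follows: "This aim is important to ensure that VRMT of the non-paretic arm does not have a negative effect on paretic arm function". Section 2.1 repeats the expectation that function will improve "without jeopardizing paretic arm function in patients with severe paresis (Aim 3"). The measure is a primary endpoint in section 1.2: "Paretic Arm Evaluation: Upper-Extremity Fugl-Meyer Assessment". Paretic work area is secondary (section 1.3).

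The analysis in section 8.3 is a linear mixed model with group, time and their interaction, and "single-degree-of-freedom linear contrasts [80] to determine if the data support our predictions (see next section"). Section 8.2 says that 60 per group "provides adequate power (≥ 0.80) to assess each prediction when the effect size" is f = 0.35 or larger, and adds: "We will go through the major measures and analyses for each aim below". No such text follows. Section 8.3 turns to lesion reconstruction, and the next section is 9.0 on confidentiality. The documents give no Aim 3 contrast, time point, margin, confidence-limit rule or alpha.

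**The concern.** Aim 3 contains two questions. Whether VRMT harms the paretic arm can be put to a difference contrast. Whether VRMT can be said not to harm it cannot be answered by that contrast coming out non-significant, because a real decline can also be non-significant. The second question is the one the prediction and the stated purpose need answered.

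The situation is a plausible one. Section 1.1 describes the pilot effect in 15 patients as a modest reduction in impairment, and a small true change may well be non-significant. The plan does not say what would then be concluded. A reader could take the null result as evidence of safety on a primary endpoint, in a trial whose background (section 2.1) cites animal work where acute-phase training of the non-paretic limb interfered with later paretic recovery.

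The missing analyses affect every aim. They matter most here because the default reading of a null contrast is the wrong one for a no-harm claim.

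**Working it through.** **Inputs.** From the documents: 60 per group and f = 0.35 (section 8.2); two pre-tests and three post-tests (section 7.3); lower UEFM is worse (severity bands in section 2.2). Assumed, because not stated: two-sided alpha 0.05, so one-sided 0.025 for a harm limit. No SD of UEFM change is given, so results are in units of that SD. The 0.3 SD decline is illustrative and is not called clinically important.

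**The plan's own figure.** For two equal groups d = 2f = 2 × 0.35 = 0.70. A two-sample t-test with 60 per group has power 0.967. The stated bound of 0.80 therefore holds under these assumptions. It concerns detecting a difference and says nothing about the decline that could be ruled out.

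**Missed harm, single change score, within VRMT (n = 60).** The noncentrality is d√n = 0.3 × √60 = 2.32, against a critical t on 59 df of 2.00. The probability of a non-significant result is 0.372.

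**Margin that can be excluded.** With a true change of zero, 80% power at one-sided 0.025 needs a noncentrality of 2.848. The margin is 2.848/√60 = 0.368 SD.

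**Using the repeated tests.** Let each test have variance σ² and equal correlation ρ. A change between means of a pre-tests and b post-tests has variance σ²(1−ρ)(1/a + 1/b).

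| Tests used | Variance / σ²(1−ρ) | SD relative to single change | Decline of 0.3 SD non-significant | Margin, 80% power |
|---|---|---|---|---|
| 1 pre, 1 post | 2 | 1 | 0.372 | 0.368 SD |
| 2 pre, 1 post | 1.5 | √0.75 = 0.866 | 0.248 | 0.318 SD |
| 2 pre, 2 post | 1 | √0.5 = 0.707 | 0.102 | 0.260 SD |

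In rows 2 and 3 the effective decline is 0.3/0.866 = 0.346 and 0.3/0.707 = 0.424, and the margins are 0.368 × 0.866 and 0.368 × 0.707. Row 3 also assumes that the effect is the same at both post-tests.

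**What a null result can still show.** If VRMT truly gives a gain of 0.2 SD, a single-change t-test is non-significant 67% of the time (42% with the averaging in row 3). In a simulation of 400,000 trials under the single-change test, 95% of those non-significant results had a 95% confidence interval that excluded a decline of 0.3 SD. The data would often be informative, and the plan lacks the rule for reading them.

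**The case against.** **The aim may be only to detect harm.** Its opening clause is, and a difference contrast suits it. The prediction and the stated purpose go further, so this answers only part of the point.

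**A clear gain needs no margin.** This is correct. A confidence interval wholly on the improvement side supports the prediction as it stands, and that is the direction of the pilot. The point is confined to other results.

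**A reader might infer that a non-significant result can never support the prediction, or that the design is too small for Aim 3.** The documents do not support either. The interval around a null estimate can exclude a stated decline, and the figures above show that within VRMT it often would.

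**The t-test figures are not the planned analysis.** This stands. Section 8.3 plans a mixed model with random coefficients. Averaging under equal correlation cuts the miss rate from 37% to 10%, but that also rests on assumptions the plan does not state. The figures show scale only.

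**A reader might treat a between-arm deficit on UEFM as the harm in question.** Prediction 1b (section 1.1) expects conventional therapy to do as well as or better than VRMT on the same scale. A deficit against it could simply confirm 1b. Aim 3 is worded about VRMT itself, which points to change within that arm. That change has no concurrent untreated control, and section 7.1 allows standard care alongside. The repeat baseline at visit 2 (section 7.2.2), in chronic-stage patients, is a useful check on stability but not a control.

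**The analysis may exist elsewhere, or the DSMB may cover it.** Section 18.4 mentions an uploaded grant, but only for a table. The point is that the analysis is absent from this plan, not that it was never written. The DSMB text gives no paretic-arm threshold.

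**Conclusion.** The point holds in this form: the plan has no valid route from a non-significant contrast to the Aim 3 conclusion, because it states no margin and no confidence-limit rule. It should be fixed. It does not show that VRMT is harmful, that the trial cannot address Aim 3, or that the stated power is wrong.

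With 60 in the VRMT group, a true 0.3 SD decline would go undetected about 37% of the time with a single change score and about 10% under favourable averaging. The excludable margin is about 0.37 or 0.26 SD. These sizes rest on the assumed alpha, SD units and correlation structure. The logical gap does not depend on them.

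**What to change.** Settle the following before any outcome analysis by arm, including the interim analyses mentioned in section 18.4.

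1. Make the within-VRMT change in UEFM from the averaged double baseline the Aim 3 contrast. Name its time point and estimate it from the planned mixed model.
2. Specify and justify a UEFM margin for that change. The study team must choose it; none is proposed here.
3. Conclude no decrement only if the harm-side limit (lower UEFM) of the 95% confidence interval excludes the margin, and never from a non-significant contrast.
4. Report the randomised between-arm difference with its interval as supportive. State that a deficit against conventional therapy is compatible with prediction 1b and is not itself a decrement. Do not attribute a within-arm change to VRMT alone.
5. For Aim 3, replace the f = 0.35 power statement with the margin that the design can exclude.

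This costs wording and one justified margin, with no new patients, visits or data. The downside is that the margin must be defended and the Aim 3 conclusion may be less favourable.

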1.2 Primary Study Endpoints

Non-Paretic Arm Evaluation: Jebsen-Taylor Hand Function Test
Paretic Arm Evaluation: Upper-Extremity Fugl-Meyer Assessment
Upper Extremity Functional Activity: Abilhand Assessment
Functional Independence: Barthel Index

1.3 Secondary Study Endpoints

Functional Independence Measure (FIM)-motor component

Kinematic Outcomes:

Positional Variance (Early and Late):

- Peak Velocity,
- End point of movement (tangential velocity minimum, after peak velocity that has an amplitude of less than 15% of maximum velocity)

Work Area (Paretic Arm)

2.0 Background

2.1 Scientific Background and Gaps

Stroke is a major health problem in the United States that leaves many survivors with chronic motor impairment, including hemiparesis in the limbs that are on the opposite side of the body to the damaged brain hemisphere. A substantial body of research has now established that the non-paretic arm often has motor deficits that limit performance of activities of daily living and thus functional independence [6, 8, 11-22]. The significance of the proposed research is that we developed a targeted remediation protocol to ameliorate persistent functional performance deficits in chronic stroke patients with severe paresis, who's non-paretic arm impairments are generally ignored in most current rehabilitation protocols. Our intervention protocol is grounded in the premise that targeted remediation of fundamental control deficits exhibited by the non-paretic arm will generalize and transfer beyond practiced tasks to functional activities and functional independence. The previous cycle of this grant detailed the mechanistic underpinnings of non-paretic arm motor deficits. The scientific premise of this proposal is based on the finding that non-paretic arm motor deficits become functionally limiting in patients with severe paresis, who are unable to use the paretic arm for manipulation [23]. This group of patients is identified by an upper extremity Fugl-Meyer (FM) score between 0-28 and a score of 0 (inability to perform) in the mass extension and prehension components of the Fugl-Meyer Assessment.

Woytowicz et al [1] recently reported a cluster analysis of 247 stroke patients, and identified a severely paretic group in the FM score range of 0-28. With the exception of mass finger flexion, 95-100%

of the patients scored 0 (unable to perform) for each item of the wrist movement, mass finger extension, and each prehension item of the FM. Thus, this severely paretic group of stroke patients is unable to use the paretic arm for manipulation purposes in activities of daily living. Deficits in coordination of the non-paretic arm can thus produce substantial limitations in the speed and efficacy of functional activities in this population. In fact, our preliminary findings (see Figure 2) indicate that unilateral tasks with the non-paretic arm take, on average, twice as long to complete as the comparable arm of age-matched control participants, indicating labored and inefficient movement that can interfere with patient's participation in activities. Unfortunately, clinical rehabilitation has yet to recognize the need to address non-paretic arm motor deficits, largely because scientific evidence has not yet been translated into clinical practice, nor has the best practice for this translation been specified through innovative intervention studies. This proposal will directly address these shortcomings, in order to provide a model for understanding how to incorporate non-paretic arm motor training into clinical rehabilitation practice for patients with severe paresis. It should be noted, however, that in animal models, training of the non-paretic arm in the acute phase of stroke recovery has been shown to interfere with subsequent paretic arm recovery [24, 25]. In addition, constraining the use of the non-paretic arm can facilitate functional recovery in those stroke survivors with mild to moderate paresis who are capable of distal manipulation in the contralesional hand, but who avoid using that arm due to learned non-use [26, 27].

Importantly, our proposed intervention focuses on patients with severe paresis who are in the chronic phase of stroke, and who do not have the sensorimotor requisites for paretic hand dexterity or manipulation. In this group of patients, recent findings indicate that intense resistance training of the non-paretic arm can reduce impairment measured in the paretic arm [10]. Consistent with this finding, our pilot data shows that intense non-paretic arm dexterity training also leads to a modest reduction in paretic arm impairment. Thus, we expect that the unilateral non-paretic arm VRMT training proposed here will improve functional independence without jeopardizing paretic arm function in patients with severe paresis (Aim 3). Our ultimate goal is to determine whether non-paretic arm remediation should be part of a package of rehabilitation that assesses and remediates fundamental control deficits in each arm of severely paretic stroke patients [4].

2.2 Previous Data

Preliminary Studies: Our findings from the previous grant cycle showed that the nature of non-paretic arm motor deficits can be explained by a model of hemispheric lateralization for motor control [64]. Thus, damage to each hemisphere produces specific and unique motor deficits in the non-paretic arm [7, 9]. *Figure 1A* shows reaching movements in the non-paretic arm of patients with left and right hemisphere damage. While patients with left hemisphere damage (LHD) made highly curved movements with accurate final positions, patients with right hemisphere damage (RHD) made straight movements with poor final position accuracies. *Figure 1B* shows the variance in hand positions during the initial trajectory phase (bottom ellipses) and in the final position (top ellipses) of the movement. This demonstrates the double dissociation between hemisphere of damage and motor control process effected by the lesion: RHD patients had deficits in stabilizing accurate final positions across trials, while LHD patients had deficits in stabilizing accurate initial trajectories across trials. We characterized these hemisphere-dependent movement deficits in studies that restricted motion to the horizontal plane; this was necessary to better control experimental variables, such as the joint displacements associated with a particular target. To achieve Aim 2, we will use this well-established horizontal reaching paradigm that yields initial positional variance (at peak velocity) and final position variance (at movement end) to assess potential training-related changes in hemisphere-specific motor deficits.

As an important foundation for the proposed research, we tested whether non-paretic arm motor function depends on the severity of paresis in the contralesional arm, and on the side of the brain that is damaged [23]. All patients were right-handed, prior to stroke. Figure 2 shows data from 54 right-handed, age and gender matched control participants, 48 right-handed LHD survivors, and 62 right-handed RHD survivors. The y-axis represents the time to complete the Jebsen-Taylor Hand Function Test (raw score). The JTHFT is a clinical assessment of unilateral arm function [65] that includes a range of

tasks that simulate the coordination requirements of functional daily activities [66, 67]. The left column in Figure 2 (control) shows the difference between healthy participants performing with the non-dominant left arm (Black) and the dominant right arm (Grey). The data are stratified on the x-axis by hand, and severity of contralesional paresis, as measured by the upper extremity component of the Fugl-Meyer Assessment of motor impairment [68] (mild [43-66], moderate [29-42], Severe [0-28]). In stroke survivors, JTHFT scores are only for the non-paretic arm (ie. Gray = non-paretic right arm of RHD participants; Black = non-paretic left arm of LHD participants). Note that the 'severe' classification in this plot reflects the level of impairment we target in this proposal.

In stroke survivors, JTHFT performance with the non-paretic arm was impacted substantially by both the severity of paresis and the side of brain damage. Participants with the most severe paresis in the contralesional arm had the greatest motor deficit in the non-paretic arm. Furthermore, the magnitude of the deficit depended on the side of the lesion, such that left hemisphere damage was associated with a 115% increase in JTFT score, while right hemisphere damage increased the time to complete the JTFT by 66%. These comparisons are relative to performance of the same arm (right or left) of age-matched control participants. However, it should be stressed that in LHD patients, the non-dominant arm must now function as a dominant controller, indicating an even larger deficit relative to age-matched dominant arm performance. Thus, stroke survivors who are forced to rely most extensively on the non-paretic arm for performance of ADL have the greatest deficits in coordination in the non-paretic arm. These stroke survivors were tested, on average, 1.8 years (± 0.3 SE) after stroke, which suggests that these deficits do not spontaneously improve over time. To provide a reference, imagine using only your non-dominant arm to carry out all your activities of daily living, such as preparing food, dressing including buttoning, putting on socks, and shoes, etc. This would be somewhat frustrating. Now imagine that your non-dominant arm has become 115% slower and less coordinated than it was—the case for our severely impaired LHD patients. RHD patients get to use the previously dominant arm, but with a 66% decrement in function. Overall, these impairments are substantially functionally limiting.

